### 4.2. Analysis Sets

For the purposes of analysis, the following analysis sets are defined:

- Intent-to-treat (ITT) Set – Includes all enrolled participants. This set will be used for efficacy analyses.
- Safety Analysis Set – Includes all enrolled participants who receive at least 1 dose of the IP. This set will be used for the safety analyses.

The full analysis set is used to analyze endpoints related to the efficacy objectives and the safety analysis set is used to analyze the endpoints and assessments related to safety.

### 4.3. Statistical Methods for Primary Safety Analyses

#### 4.3.1. Adverse Events

Adverse events (AEs) are collected from the time of informed consent/assent through the defined follow-up period. AEs are coded using MedDRA dictionary, version 24.0 and are

categorized by system organ class (SOC) and preferred term (PT). A treatment-emergent AE (TEAE) is defined as an AE that starts or worsens on or after the first day of dosing with IP. Detailed by-patient listings of all AEs reported during the study will be provided and will include verbatim and coded terms for each AE.

For the safety Analysis Set, the following tabular summaries will be created:

- An overall summary of TEAEs will present the number and percentage of subjects with at least 1 reported TEAE, study drug related TEAE, serious TEAE, TEAE of Grade 3 or higher, study drug infusion interruption, and death
- TEAEs by system organ class and preferred term
- TEAEs by system organ class, preferred term, and maximum severity
- Study drug related TEAEs by system organ class and preferred term
- TEAEs by decreasing frequency of preferred term
- Moderate or severe TEAEs by system organ class and preferred term
- Moderate or severe study drug related TEAEs by system organ class and preferred term
- TEAEs that led to study drug infusion interruption by system organ class and preferred term
- Serious TEAEs by system organ class and preferred term
- Serious study drug related TEAEs by system organ class and preferred term

For incidence reporting, if a subject reported more than 1 AE that was coded to the same preferred term/system organ class, the subject will be counted only once for that specific preferred term/system organ class. For TEAEs presented by severity, the worst severity for each event during the clinical trial will be presented for each subject. If the severity is missing for a TEAE, then a severity of “Severe” will be assigned. The imputed values for severity assessment will be used for incidence summaries, while the actual values will be used in data listings.

For TEAEs presented by relationship to study drug, the closest relationship to study drug for each event during the clinical trial will be presented for each subject. If the relationship to investigational product is missing for a TEAE, a causality of “Related” will be assigned. The imputed values for relationship assessment will be used for incidence summaries, while the actual values will be presented in data listings.

All AEs, SAEs, TEAEs leading to study drug interruption, and SAEs leading to death will be displayed in separate listings.

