# **7 DISCONTINUATION OF STUDY INTERVENTION AND PARTICIPANT DISCONTINUATION/WITHDRAWAL**

## **7.1 Discontinuation of Study Intervention**

In rare instances, it may be necessary for a participant to permanently discontinue study intervention. If the IP is discontinued at any time, participants should follow the 2-week taper schedule unless otherwise medically indicated such, as drug-induced rash. If the participant discontinues the IP, evaluations listed for the Early Termination Visit (Visit 13 [Week 156]; as shown in the SOA [Table 1]) are to be performed as completely as possible along with the end of study and safety follow-up assessment, as appropriate. Comments (spontaneous or elicited) or complaints made by the participant must be recorded in the source documents. The reason for termination, date of stopping IP, and total amount of IP taken must be recorded in the eCRF and source documents. Discontinuation of IP due to AEs must also be reflected on the AE eCRF page. Participants who discontinue IP should undergo a 2-week or shorter taper period, as clinically indicated. These participants will have a visit 2 weeks after the end of taper to complete the safety follow-up assessments.

The reason for early discontinuation of the IP must be determined by the investigator and recorded in the participant's source documents and on the eCRF. If a participant is withdrawn for more than 1 reason, each reason should be documented in the source document and the most clinically relevant reason should be entered on the eCRF.

Reasons for early termination include but are not limited to the following:

- AE (including pregnancy).
- Protocol violation/protocol deviation.
- Withdrawal by participant or parent(s)/LAR(s).
- Lost to follow-up.
- Lack of efficacy.
- Death.
- Investigator decision.

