### **9.2.5 Safety Analyses**

All safety analyses will be performed in the Safety Population. The results will be summarized overall and by the treatment received in the parent study (placebo or GNX).

The number and percentage of days participants received IP, the highest percentage of the maximum allowable daily dose (1800 mg or 63 mg/kg) participants received, and the total amount of IP received will be summarized.

A participant data listing will be provided with full details of the study drug dispensation.

Safety assessments include:

- AEs.
- Vital signs including BP, HR, RR, body temperature, height, and body weight.
- Physical, neurological, and developmental examinations.
- 12-lead ECG.
- Clinical laboratory tests.
- Concomitant ASM levels (as detailed in Section 8.3.6).
- C-SSRS.

Detailed analysis and complete listings will be outlined in the SAP.

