### **2.3. Study Endpoints**

#### **2.3.1. Primary Endpoint**

The primary endpoints are the following safety endpoints:

- Incidence and severity of AEs, SAEs and withdrawals and dose-reductions due to AEs

- Vital sign measurements including blood pressure, heart rate, respiratory rate, body temperature, height, and body weight
- Physical, neurological, and developmental examination
- 12-lead ECG
- Clinical laboratory tests
- C-SSRS.

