## **5.4. Subject Disposition**

The number of patients screened for this study, the number of rollover (from TSC-2001 and 3001) and the number of patients who received at least one dose of IP will be summarized. The final disposition of all patients who receive IP will be summarized. Reasons for discontinuation of study participation will be summarized. The total number and percentage of patients who complete the study will be summarized.

A listing of patient disposition will be provided. In addition, a summary of the number of patients included in each analysis set will be presented.

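### SAP 4.3.1 plans no incidence of TEAEs leading to dose reduction, and AE-led withdrawals are counted only by a single disposition reason, although both belong to the first primary endpoint

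*SAP*

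**What the plan says.** **Endpoint.** SAP 2.3.1 and Protocol 9.2.2 give the same first primary endpoint: "Incidence and severity of AEs, SAEs and withdrawals and dose-reductions due to AEs". Protocol 9.2.5 leaves the detail to the SAP: "Detailed analysis and complete listings will be outlined in the SAP".

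**AE tables.** SAP 4.3.1 lists an overall summary and nine further tables. The overall summary ends with "TEAE of Grade 3 or higher, study drug infusion interruption, and death". The only table tied to an action on study drug is "TEAEs that led to study drug infusion interruption by system organ class and preferred term".

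**AE listings.** The same section plans four: "All AEs, SAEs, TEAEs leading to study drug interruption, and SAEs leading to death will be displayed in separate listings".

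**Disposition.** SAP 5.4 adds: "Reasons for discontinuation of study participation will be summarized". Protocol 7.1 says that where there are several reasons, "the most clinically relevant reason should be entered on the eCRF". It also says: "Discontinuation of IP due to AEs must also be reflected on the AE eCRF page".

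**Exposure.** SAP 5.7 summarizes time on treatment, share of days dosed, highest daily dose and cumulative dose. It adds a by-patient listing that shows why a dose was changed.

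**The concern.** Tolerability is part of the primary objective. In a descriptive, single-arm extension the planned tables are the analysis, so a named component of a primary endpoint with no planned count is not reported in any usable sense. Dose adjustment is one of the protocol's means of managing tolerability (Protocol 6.2), which makes AE-led dose reductions a direct tolerability outcome.

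The event term matters too. Protocol 2.3.1 reports AE-led discontinuation in earlier placebo-controlled studies by term (dizziness, somnolence, fatigue). The SAP text plans no comparable table for this study, so the long-term experience could be set beside those figures only by reading listings patient by patient.

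**Working it through.** No formula applies and the plan states no figure to reproduce. The check sets each part of the endpoint against every planned output.

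**Step 1: count the outputs in SAP 4.3.1.**

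- Overall summary, 6 items: any TEAE, related, serious, Grade 3 or higher, interruption, death. Items on dose reduction, IP discontinuation or withdrawal: 0 of 6.
- Further tables, 9: all TEAEs by SOC/PT; by maximum severity; related; by PT frequency; moderate or severe; moderate or severe and related; interruption; serious; serious and related. Tables on dose reduction, discontinuation or withdrawal: 0 of 9.
- Separate listings, 4: all AEs plus 3 subsets (SAEs, interruption, fatal SAEs). Subsets on dose reduction, discontinuation or withdrawal: 0 of 3. The all-AEs listing contains the events but does not count them.

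**Step 2: look for substitutes elsewhere in the SAP.**

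| Endpoint component | Planned output | What it gives |
|---|---|---|
| AEs | SAP 4.3.1 | Incidence and severity |
| SAEs | SAP 4.3.1 | Incidence by SOC/PT |
| Withdrawals due to AEs | SAP 5.4 | Count by reason, no event term |
| Dose reductions due to AEs | SAP 5.7 | By-patient listing only, no count |

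**Step 3: dose reductions.** None of the SAP 5.7 summary measures identifies a reduction. Someone whose dose is cut after reaching their highest level keeps the same maximum daily dose, and a low cumulative dose may equally reflect early exit or a lower starting dose. Only the listing shows the reason, and a listing is not an incidence.

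**Step 4: withdrawals.** Protocol 7.1 includes AE among the reasons for early termination, and SAP 4.1 presents categorical data as counts and percentages. SAP 5.4 therefore does give an incidence of AE-led withdrawal. It has two limits. With one reason per participant, an AE that contributed but was not judged the leading reason is not counted. And nothing in that summary says which event was responsible.

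**Step 5: fit of the existing wording.** Protocol Table 2 and SAP Section 1 describe an oral suspension, so infusion is the wrong word in both the overall summary and the table. Protocol 10.4.3 rates intensity as mild, moderate or severe, and SAP 4.3.1 itself uses that scale in its other severity tables. The Grade 3 item has no defined meaning on it.

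**The case against.** The strongest reply concerns withdrawals. A reader might infer that AE-led withdrawals go uncounted altogether. They do not: SAP 5.4 counts them by reason. The endpoint does not say whether withdrawal means stopping study drug or leaving the study, but this has little practical effect. Under Protocol 7.1 and 7.2 both routes lead to the Early Termination Visit and safety follow-up, and under Protocol 4.4 participation ends once that visit is done, so the two counts should nearly coincide. What remains is the single-reason limit and the missing event term.

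A reader might also infer that the endpoint requires a severity breakdown of withdrawals and dose reductions. Severity can be read as applying to AEs and SAEs only, so that is not established. Nor does the endpoint mention SOC or PT; tables at that level are the natural companion to the other AE tables, not an explicit commitment.

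On importance, the worked case in Protocol 6.2 concerns AEs during titration, and its first option is to hold the dose. Extension participants enter on a dose already set in the parent study, so reductions may be less frequent than in the titration phase. The documents give no rate for this study.

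Finally, the shells are a separate document (SAP Sections 7 and 8) and may contain the missing tables. That limits the point to the SAP text, but SAP 4.3.1 states which summaries will be made, and these are not among them.

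**Conclusion.** The point holds for the SAP text. There is no planned incidence of TEAEs leading to dose reduction, although the first primary endpoint names it. AE-led withdrawals have a disposition count, but by a single reason that can understate AE involvement and without the event term. The one action on study drug that is tabulated, interruption, is not in the endpoint and is misdescribed.

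The size is the coverage count: 0 of 6, 0 of 9 and 0 of 3. A reader might want to gauge it from the Phase 2 parent study, where Protocol 2.2.2.2 reports 4 AE-led discontinuations among 24 screened, or from the rates by event in Protocol 2.3.1. Those figures do not measure this gap: they come from other settings, and entrants here have already come through a parent study.

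Nor should the point be read as a claim of bias or lost data. The study is descriptive, no estimate is distorted, and the information appears to be collected. It rests on two assumptions: that the disposition page carries one reason per participant, as Protocol 7.1 describes for early discontinuation, and that the SAP text is the governing specification. It should be fixed before lock; it does not threaten the study.

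**What to change.** In SAP 4.3.1, add to the overall summary, and as SOC/PT tables:

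- (a) TEAEs leading to dose reduction;
- (b) TEAEs leading to permanent IP discontinuation or study withdrawal, with a sentence stating which of the two the endpoint's term covers.

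Derive both from the action taken with study drug on the AE record. Protocol 7.1 requires AE-led discontinuation to appear on the AE eCRF page, and Protocol 8.4.6 describes an event-level action whose examples include interrupted, reduced and withdrawn. Confirm the field in CRF v6.0, which was not available for this review. If no reduction category exists, fall back on the recorded reason for dose change (SAP 5.7) with the dose-reduction dates (Protocol 6.5), and state the rule for linking a reduction to an AE term.

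Replace infusion interruption with IP interruption in both tabular items. Reconcile the Grade 3 item with the protocol's three-level scale. Simply substituting severe is not enough: Protocol 10.4.3 defines severe as falling short of an immediate threat to life and offers no higher category, so the SAP must say where life-threatening events are counted.

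The cost is SAP wording and a few table shells before database lock. If the CRF field is confirmed, no new data collection is needed.

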#### **4.3.2. Clinical Laboratory Evaluations**

Laboratory data collected in this study include serum chemistry and hematology values, and urinalysis results. The baseline laboratory value is defined as the last value observed prior to the first administration of study drug, typically Visit 1, the first visit of the OLE. Any values collected after the administration of study drug are regarded as post-baseline. Change from baseline will be calculated as the post-baseline value minus the baseline value. Only the numeric part in laboratory values that contain non-numeric qualifiers, such as less than (<) a certain value or greater than (>) a certain value, will be used in the summary statistics.

Laboratory values and change from baseline in these values will be listed and summarized for patients in the Safety Analysis Set by group (chemistry, hematology or urinalysis) and by visit. Listings of patients with positive drug screen or pregnancy results will be provided.

Descriptive summaries of continuous laboratory values and change from baseline in these values will include the number of observations, mean, SD, median, minimum and maximum values at each time point. Data will be summarized in SI units. Shift tables comparing baseline classification based on reference range (i.e., normal, low, or high) to the worst classification recorded post-baseline will be presented. In the case that a patient has both “low” and “high” post-baseline results for the same laboratory parameter, the patient will be counted under both “low” and “high”. A patient will be counted under the “normal” category post-baseline only if all post-baseline results are categorized as “normal”.

For non-numeric urinalysis data, a shift table comparing baseline results (negative, trace or positive) to the maximum post-baseline result will be presented.

Listings of laboratory results for each patient will be presented. Values outside of the laboratory’s reference range will be flagged in the listing. A by-patient listing of laboratory values outside the normal reference range for the parameter will be produced.

#### **4.3.3. Vital Signs, Physical, Neurological and Developmental Examination Findings**

##### Vital Signs

Vital signs measured in this study include systolic and diastolic blood pressure, heart rate, respiratory rate, and body temperature. Baseline for vital signs will be the values obtained at the last assessment prior to the first dose of IP, typically Visit 1, the first visit of the OLE. Change from baseline is calculated as the post-baseline value minus the baseline value. Missing values will not be imputed.

Absolute values and changes from baseline in vital signs at each visit will be summarized in the Safety Population using descriptive statistics (n, mean, SD, median, minimum, and

maximum). A by-patient, by-visit listing of vital signs collected and height and weight recorded will be provided.

All vital signs included the parameter values and overall interpretations will be listed. Changes from baseline physical examination findings will also be listed individually by patient.

The observed data at baseline and change from baseline for each measurement day will be summarized for each parameter with descriptive statistics. Plots of mean vital signs values (and standard error bars) over week 4 will be produced.

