### **8.3.2 Vital Signs**

Vital signs including heart rate (HR [bpm]), respiratory rate (RR [breaths/minute]), body temperature measured orally or on the skin, and blood pressure (BP [mmHg]) will be collected at every in-clinic visit.

BP and pulse measurements will be assessed in a sitting position with a completely automated device. Manual techniques will be used only if an automated device is not available.

BP and pulse measurements should be preceded by at least 5 minutes of rest for the participant in a quiet setting without distractions (eg, television, cell phones).

Vital signs will be measured in a sitting position after 5 minutes rest and will include temperature, systolic and diastolic BP, pulse, and RR. Three readings of BP and pulse will be taken. The first reading should be rejected. The second and third readings should be averaged to give the measurement to be recorded.

Vital signs, body temperature, height, and weight will be collected at Visit 1 (First Visit of the OLE), Visit 3 (Week 26), Visit 5 (Week 52), Visit 7 (Week 78), Visit 9 (Week 104), Visit 11 (Week 130), Visit 13 (Week 156), and Visit 14 (Week 160).

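### SAP 4.3.3 does not explicitly plan any change-from-baseline summary of height or body weight, although both belong to the vital-sign primary safety endpoint, and its vital-sign plots refer to a Week 4 that the schedule does not contain.

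*SAP*

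**What the plan says.** **Endpoint.** SAP 2.3.1 includes among the primary endpoints "Vital sign measurements including blood pressure, heart rate, respiratory rate, body temperature, height, and body weight". Protocol Section 3 says the same. Protocol 9.2.5 repeats it among the safety assessments, "Vital signs including BP, HR, RR, body temperature, height, and body weight", and leaves the detailed analysis to the SAP.

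**Collection.** Protocol 8.3.2 and the Schedule of Activities (Table 1) have height and weight measured at Visits 1, 3, 5, 7, 9, 11, 13 and 14.

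**Analysis.** SAP 4.3.3 begins: "Vital signs measured in this study include systolic and diastolic blood pressure, heart rate, respiratory rate, and body temperature". The main output follows: "Absolute values and changes from baseline in vital signs at each visit will be summarized in the Safety Population using descriptive statistics". The next sentence is the only one in that section to mention height and weight: "A by-patient, by-visit listing of vital signs collected and height and weight recorded will be provided". Later the section adds: "The observed data at baseline and change from baseline for each measurement day will be summarized for each parameter with descriptive statistics". It ends with the figures: "Plots of mean vital signs values (and standard error bars) over week 4 will be produced".

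**Elsewhere in the SAP.** Section 5.3 summarises height, weight and BMI as demographic characteristics. Section 6 declares no departure from the protocol's analyses on this point. Section 8 places the table shells in a separate document.

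**The concern.** The endpoint definition and the analysis section of the same SAP do not match. A programmer who takes 4.3.3 as it reads would produce by-visit change tables for blood pressure, heart rate, respiratory rate and temperature, and a listing for height and weight. Part of a primary endpoint would then have no summary of how it changes.

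This matters more here than in a short adult study. The primary objective is long-term safety in children and adults, participation can last about 3 years, and the planned age groups start at 1 year. A listing shows individual values but no group trend. A summary of raw change would also be hard to interpret in participants who are still growing, because there is no control arm to show what normal growth would have been.

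The Week 4 plot is a separate slip in the same section. It affects the figures for every vital sign, and it is not evidence on the height and weight question.

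**Working it through.** The plan states no figure to reproduce, and no power or alpha calculation applies. The check is a comparison of text and a count.

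**1. Endpoint against parameter list.**

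| Measure | In endpoint (SAP 2.3.1) | In opening list of SAP 4.3.3 | Output that names it explicitly |
|---|---|---|---|
| Blood pressure | yes | yes | values and change by visit |
| Heart rate | yes | yes | values and change by visit |
| Respiratory rate | yes | yes | values and change by visit |
| Body temperature | yes | yes | values and change by visit |
| Height | yes | no | listing (4.3.3); demographics (5.3) |
| Body weight | yes | no | listing (4.3.3); demographics (5.3) |

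Six measures are in the endpoint and four are in the analysis list: 6 − 4 = 2 left out.

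**2. Data available.** The collection weeks are 0, 26, 52, 78, 104, 130, 156 and 160. That is 8 time points, of which 8 − 1 = 7 are post-baseline. Explicitly planned post-baseline or change summaries of height or weight over those 7 time points: 0.

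**3. Does the sentence about each parameter bring them in?** It comes soon after a sentence on listing vital signs and their parameter values, so a parameter there most naturally means a vital-sign parameter as listed at the start of the section. The listing sentence also points this way: it names height and weight in addition to the vital signs collected, which would be redundant if the term already covered them. The opening paragraph of protocol 8.3.2 likewise describes vital signs as heart rate, respiratory rate, temperature and blood pressure. On the other side, SAP 2.3.1, protocol 9.2.5 and the vital-sign row of Table 1 all count height and weight as vital signs. The text favours exclusion without settling it.

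**4. Do other outputs fill the gap?**
- SAP 5.3 describes participants' height, weight and BMI as demographic characteristics. It plans no change over time.
- The listing gives no group mean, spread or trend.
- Protocol 8.4.5 lets a clinically significant change in a vital sign be recorded as an adverse event, and SAP 4.3.1 tabulates treatment-emergent events. That route depends on an investigator's judgement of one participant at a time, so a gradual shift across the group could pass below it.

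**5. The plot.** Table 1 runs from Week 0 to Week 13 and then at 13-week intervals to Week 156, followed by the safety follow-up. No visit falls at Week 4. Week 13 is a phone visit without vital signs, so the first post-baseline values are at Week 26. Taken as written, the figure has no scheduled post-baseline data to show.

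**The case against.** The strongest reply is that this is a drafting matter and the tables may well exist. The opening list in 4.3.3 is introduced as an inclusion, which need not be exhaustive. SAP 2.3.1 classes height and weight as vital-sign measurements, a later sentence promises change from baseline for each parameter, and Section 6 declares no departure from the protocol. The shells could settle the point, and they are not part of the documents. This stands to the extent that the omission cannot be called certain. It does not remove the need for a correction: whether part of a primary endpoint gets a summary table should not rest on how a programmer reads one word.

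A reader might go further and infer that height and weight are never summarised, or that growth goes unassessed and an effect on it could not be seen. The documents do not support that. SAP 5.3 does summarise both measures, though only as demographics. The data are collected at 8 visits and listed by patient and visit, and clinically significant changes can be reported as adverse events.

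Nor do the documents allow the consequence to be sized in kilograms. They give no growth rate, no expected weight effect and no share of children among participants, and the protocol's risk assessment (2.3.1) describes CNS effects and raises no growth or weight signal.

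Finally, neither document calls for z-scores. Their absence contradicts nothing in the plan; they are a recommendation.

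**Conclusion.** The point holds in a limited form. SAP 2.3.1 and 4.3.3 are inconsistent: 2 of the 6 measures in the vital-sign primary endpoint, collected at 7 post-baseline visits, have no explicitly planned summary of change. This rests on the natural reading of 4.3.3; the broader reading is possible and cannot be excluded without the shells. The Week 4 plot wording does not fit the schedule on any reading.

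The SAP should be amended on both counts before database lock. The first has some weight because it touches a primary endpoint in a single-arm study of about 3 years that includes growing children. It does not threaten the study's validity, since the data are collected and the analysis can still be specified.

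**What to change.** 1. In SAP 4.3.3, add height and body weight to the vital-sign parameters, and state that observed values and change from baseline will be summarised at each visit at which they are collected.
2. For participants under 18, also summarise age- and sex-standardised z-scores for height and weight and the change in them. In a single-arm study, raw change mixes normal growth with any drug effect. The age split at 17 years already used in SAP 5.3 can serve.
3. Replace the Week 4 wording with plots over the scheduled vital-sign visits from Week 0 to Week 160, so that the safety follow-up visit is included.
4. Make the table shells agree.

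The cost is a few sentences of SAP text and two or so tables on data already collected. A growth reference must be chosen and named in advance. Z-scores also have a limit that should be stated with the results: they compare participants with an outside reference, so a change in them does not by itself separate drug effect from disease or co-medication.
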